## 6.2 Preparation/Handling/Storage/Accountability

1. The Investigator or designee must maintain a log to confirm appropriate temperature conditions have been maintained during transit for all study treatments received and any discrepancies are reported and resolved before use of the study treatment.
2. Only participants enrolled in the study may receive study treatments and only authorized site staff may supply or administer study treatments. All study treatments must be stored in a secure, environmentally controlled, and monitored (manual or automated) area in accordance with the labeled storage conditions with access limited to the Investigator and authorized study staff.
3. The Investigator is responsible for study treatment accountability, reconciliation, and record maintenance (i.e., receipt, reconciliation, and final disposition records).
4. Unused or partially used study treatment will be returned to the Banner University Medical Center Investigational Pharmacy for destruction.

## 6.3 Measures to Minimize Bias: Randomization and Blinding

All participants (if AHI >5 on screening PSG) will be randomized to receive both high dose ato-oxy and low dose ato-oxy in random order. Each participant will be assigned a unique number

(randomization number) that encodes the participant's assignment to 1 of the 2 treatment orders of the study, according to the randomization schedule generated using a validated computer program.

Study treatment will be dispensed after PSG screening, as summarized in Section 1.3.

Returned study treatment should not be redispensed to the participants.

In case of an emergency, the Investigator has the sole responsibility for determining if unblinding of a participant's study treatment assignment is warranted. Participant safety must always be the first consideration in making such a determination. If a participant's study treatment assignment is unblinded, the DSMB must be notified within 24 hours after breaking the blind. The date and reason that the blind was broken must be recorded in the source documentation and electronic case report form (eCRF), as applicable.

Participants will be randomly assigned in a 1:1 equal allocation ratio (stratified by age 6-12 and 13-17) to receive 1 of 2 different study treatment orders, using permuted blocked randomization. Investigators will remain blinded to each participant's assigned study treatment throughout the study.

In the event of a Quality Assurance audit, the auditor(s) will be allowed access to unblinded study treatment records at the site(s) to verify that randomization/dispensing has been done accurately.

## **6.4 Study Treatment Compliance**

Participants will be required to return any unused study treatment capsules at Visit 2 and 3. Unused capsules will be counted and recorded by study personnel to assess study treatment compliance.

## **6.5 Concomitant Therapy**

Concomitant therapy with the following medications is disallowed:

- MAOIs or other drugs that affect monoamine concentrations (e.g., rasagiline) [MAOIs are contraindicated for use with atomoxetine]
- CYP2D6 inhibitors
- Strong CYP3A4 inhibitors (e.g., ketoconazole)
- Benzodiazepines and other anxiolytics

- Opioids
- Sedatives including nonbenzodiazepine “Z-drugs” (zolpidem, zaleplon, eszopiclone)
- Muscle relaxants
- Pressor agents
- Drugs with clinically significant cardiac QT-interval prolonging effects
- Drugs known to lower seizure threshold (e.g., chloroquine)
- Antiepileptics
- Antiemetics
- Modafinil or armodafinil
- Anticholinergics and anticholinesterase inhibitors, including drugs with substantial anticholinergic side effects, (e.g., first generation antihistamines)
- Sedating antihistamines
- Pseudoephedrine, phenylephrine, oxymetazoline

Medications that do not have substantial effects on the central nervous system (CNS), respiration, or muscle activity are generally allowed if dose and frequency is stable for 3 months prior to enrollment and during the course of the study, including, but not necessarily limited to, the following drugs and drug classes:

- Antihypertensives (angiotensin-converting-enzyme/angiotensin II receptor blocker inhibitors, calcium channel blockers, spironolactone, hydrochlorothiazide, etc.)
- Statins
- Proton pump inhibitors and histamine h2 receptor blockers
- Over-the-counter (OTC) antacids
- Non-sedating antihistamines (e.g., cetirizine, loratadine)
- Melatonin
- Non-steroidal anti-inflammatory drugs and acetaminophen
- Laxatives
- Inhaled corticosteroids (e.g., fluticasone)

- Antidiabetics
- Ocular hypotensives and other ophthalmics (e.g., timolol)
- Hormonal therapy (e.g., estrogen replacement or anti-estrogens) and hormonal contraceptives
- Thyroid medications
- Anticoagulants
- OTC topicals (e.g., topical pain relievers)
- Patients currently on medications for Attention Deficit Hyperactivity Disorder will be included, but should not change their medication regimen/dosage during the study.

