### **2.2.3 Biological Rationale**

Atomoxetine is a pre-synaptic norepinephrine reuptake inhibitor indicated for the treatment of attention deficit hyperactivity disorder in children and adults. Oxybutynin is an antispasmodic drug that inhibits the muscarinic action of acetylcholine on smooth muscle and is indicated for the treatment of symptoms of bladder instability associated with voiding in patients with uninhibited neurogenic or reflex neurogenic bladder such as urgency, frequency, urinary leakage, urge incontinence and dysuria.

Efficacy of the combination of these 2 small molecules for the signs and symptoms of OSA has been previously evaluated in a small number of patients in National Institutes of Health-supported studies in the academic setting. The pharmacokinetics (PK) of the atomoxetine and oxybutynin combination have recently been studied in a Phase 1 clinical program sponsored by Apnimed. New research in animals improved understanding of the state-dependent neurotransmitters involved in pharyngeal muscle activation during sleep, namely that both noradrenergic and antimuscarinic processes are involved. Specifically, the loss of noradrenergic activity is now thought to play a key role in the sleep-related hypotonia of pharyngeal muscles during non-rapid eye movement (NREM) sleep and muscarinic activity is involved in rapid eye movement (REM) atonia.

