### 5.2 Exclusion Criteria

Participants are excluded from the study if any of the following criteria apply:

Exclusion Criteria at study entry (prior to baseline polysomnography)
1. Presence of central sleep apnea on polysomnography (central AHI $\geq 5$ )

2. Currently using and adherent to PAP therapy (>4 hours per night for 70% of nights in the past 30 days based on device download or parent report)

3. MAO inhibitor use

4. Urinary retention

5. Prematurity < 37 weeks estimated gestational age

6. Seizure disorder

7. Untreated or inadequately treated hypothyroidism

8. Significant traumatic brain injury

9. Congenital heart disease and not cleared to participate by the patient's cardiologist

10. History of current, untreated depression

11. History of liver disease

12. 3+ or greater tonsillar hypertrophy

13. Positive urine pregnancy test

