## **6.6 Dose Modification**

Through protocol amendment, planned doses may be decreased on an individual or group basis according to emerging safety and tolerability data.

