### **7.3 Participant Discontinuation/Withdrawal from the Study**

- A participant may withdraw from the study at any time at his/her own request or may be withdrawn at any time at the discretion of the Investigator for safety, behavioral, or administrative reasons.
- If the participant withdraws consent for disclosure of future information, the Sponsor may retain and continue to use any data collected before such a withdrawal of consent.
- All participants who withdraw from the study with an ongoing AE must be followed until the event is resolved or deemed stable.
- Participation may be terminated before completing the study and the reason recorded as follows:
  - Withdrawal due to AE
  - Withdrawal due to incident abuse, diversion, or misuse of the study treatment
  - Loss to follow-up
  - Participant withdrew consent at own request
  - Other

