#### **8.5 Treatment of Overdose**

For this study, any dose of atomoxetine greater than 80 mg and of oxybutynin greater than 5 mg more frequently than QHS will be considered an overdose.

In the event of an overdose, the Investigator should refer to the approved product label for advice on overdose and:

1. Closely monitor the participant for AE/SAE.
2. Document the quantity of the excess dose as well as the duration of the overdosing in the eCRF.

Decisions regarding dose interruptions or modifications will be made by the Investigator based on the clinical evaluation of the participant.

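### The flat 80 mg overdose line in Section 8.5 misses a doubled full high dose of atomoxetine in children up to about 33.3 kg, and Section 6.5 conflicts with itself on children already taking atomoxetine

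*Combined protocol and SAP*

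**What the plan says.** **Overdose.** Section 8.5 states that "any dose of atomoxetine greater than 80 mg and of oxybutynin greater than 5 mg more frequently than QHS will be considered an overdose". When that definition is met, the investigator is to watch the child closely for adverse events and to record the size and duration of the excess in the eCRF. Dosing itself is by weight (Section 4.1): 0.5 mg/kg up to 40 mg throughout the low-dose period and in the first week of the high-dose period, then 1.2 mg/kg up to 80 mg. Section 6.1 gives one atomoxetine and one oxybutynin capsule each night from blister packs, with liquid as an alternative. Section 10.2 does not make overdose in itself a reportable adverse event unless it is intentional with possible self-harm; symptoms that follow a suspected overdose are reportable.

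**Children on ADHD medication.** Section 6.5 disallows "MAOIs or other drugs that affect monoamine concentrations (e.g., rasagiline"), a class wording that does not name atomoxetine. Its list of permitted drugs opens with "Medications that do not have substantial effects on the central nervous system (CNS), respiration, or muscle activity are generally allowed" and ends with "Patients currently on medications for Attention Deficit Hyperactivity Disorder will be included, but should not change their medication regimen/dosage during the study". Section 2.2.3 says: "Atomoxetine is a pre-synaptic norepinephrine reuptake inhibitor indicated for the treatment of attention deficit hyperactivity disorder in children and adults". The only drug use that Section 5.2 excludes is "MAO inhibitor use".

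**The concern.** A fixed milligram line does not fit weight-based dosing in children aged 6 to 17. In a small child, twice the full dose can lie below a line set at the adult-sized cap. An accidental double without symptoms is then not an overdose under 8.5, and because 10.2 does not report overdose as such, the plan gives no instruction to monitor that child closely or to record the excess.

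The second issue is an eligibility question. A site that screens a child on prescribed atomoxetine finds one line in 6.5 that appears to bar the child and another that appears to admit the child on an unchanged dose. If the site follows the second line, the child takes study atomoxetine on top of prescribed atomoxetine. What is at stake in both parts is clear safety instruction, not the efficacy comparison.

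**Working it through.** **Inputs.** Overdose line: more than 80 mg (8.5). With w the weight in kg, low dose = min(0.5w, 40) mg and full high dose = min(1.2w, 80) mg (4.1). Each period has 28 nights (1.1), and the first 7 nights of the high-dose period are at the low dose (4.1). One atomoxetine capsule is taken per night (6.1). The documents give no body weights and no capsule strengths, so exact mg/kg dosing is assumed. The 80 mg line is a stated definition, so there is no figure of the plan's own to reproduce.

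**1. Doubled capsule at full high dose.** This applies on 28 − 7 = 21 nights. Twice the dose is 2 × 1.2w = 2.4w mg, or 2.4 mg/kg. It exceeds 80 mg only if w > 80/2.4 = 33.3 kg.

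| Weight (kg) | Full high dose (mg) | Doubled (mg) | Overdose under 8.5? |
|---|---|---|---|
| 20 | 24 | 48 | no |
| 30 | 36 | 72 | no |
| 33.3 | 39.96 | 79.9 | no |
| 33.4 | 40.08 | 80.2 | yes |
| 40 | 48 | 96 | yes |

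A 20 kg child would have to take more than 80/24 = 3.3 times the full high dose, that is more than 80/20 = 4 mg/kg, before 8.5 applied.

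**2. Doubled capsule at 0.5 mg/kg.** This applies on 28 + 7 = 35 of 56 nights. Twice the dose is 2 × min(0.5w, 40) = min(w, 80) mg, which is never above 80 mg, so it is not an overdose at any weight. But min(w, 80) is also never above the planned high dose, min(1.2w, 80): it is lower below 80 kg and equal from 80 kg up. The child takes at most 1.0 mg/kg, against a planned 1.2 mg/kg that is itself capped at 80 mg.

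**3. The two lines of 6.5.** Atomoxetine is a norepinephrine reuptake inhibitor (2.2.3), so the monoamine bar reaches it on a literal reading. It is also an ADHD drug (2.2.3), so the ADHD line reaches it too. The bar is a class rule; the ADHD line is specific and excepts no drug. Neither says which prevails.

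**4. Size if the ADHD line were followed.** Assume the child's own dose is 0.5 to 1.2 mg/kg/day; the documents give no such figure. At full high dose and up to 80/1.2 = 66.7 kg, the total is 0.5 + 1.2 = 1.7 to 1.2 + 1.2 = 2.4 mg/kg, or 1.4 to 2.0 times the 1.2 mg/kg target. At the 0.5 mg/kg study dose the total is 1.0 to 1.7 mg/kg, above target only if the child's own dose exceeds 1.2 − 0.5 = 0.7 mg/kg.

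**The case against.** **On the overdose line.** A plausible accident is repeating a whole night's pair of capsules. That also doubles oxybutynin to 10 mg, and the oxybutynin part of 8.5 may catch it. This stands as a limit on the point, although the wording is unclear: it can be read as requiring both an amount above 5 mg and dosing more often than nightly, and the word joining the two drugs can be read as requiring both. Returned capsules are counted (6.4), but only at Visits 2 and 3. A double offset by a missed night leaves the count unchanged, and 6.4 describes no check on liquid.

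A reader might infer from the 35 of 56 nights that a harmful excess goes unnoticed for most of the trial. The documents do not support that: on those nights a doubled capsule never exceeds a dose that the trial plans to give. What remains is that it bypasses the titration that Section 4.3 introduces to limit adverse effects.

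**On ADHD medication.** A reader might infer that the protocol permits double atomoxetine. It does not clearly do so. The monoamine bar literally covers the drug, and the permitted list is introduced as covering drugs without substantial effects on the nervous system or muscle, which hardly describes a drug given here to raise airway muscle tone. But the ADHD line must already override that introduction and the bar for some drugs, so the conflict is real. Use would be seen, since medication is recorded at Visit 1 (1.3). Dose reduction is provided for as "Through protocol amendment, planned doses may be decreased on an individual or group basis according to emerging safety and tolerability data". Otherwise the investigator may change a child's management after a clinically significant finding (7.1), interrupt or modify dosing once an overdose is recognised (8.5), or use the provision that a participant "may be withdrawn at any time at the discretion of the Investigator for safety, behavioral, or administrative reasons". These are discretionary or reactive routes; none is an entry rule.

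**Conclusion.** The point holds and is minor. The main part is the overdose definition: for the atomoxetine capsule alone, on the 21 full-high-dose nights, a double of 2.4 mg/kg falls outside 8.5 in children up to about 33.3 kg. That cut-off assumes exact mg/kg dosing; rounding to capsule strengths would move it slightly. How many children are that light cannot be told from the documents.

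The secondary part is an unresolved conflict within 6.5 and a missing named exclusion in 5.2. It depends on how two lines are read together, so it is less certain than the arithmetic.

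Two stronger conclusions are not supported. The documents give no toxicity threshold, so no degree of harm can be stated. And nothing here shows an effect on the high-versus-low comparison of obstructive AHI.

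**What to change.** **Section 8.5.** Define atomoxetine overdose as more than one study atomoxetine capsule, or more than the dispensed liquid dose, in one night. This catches every doubled capsule at any weight and can be applied without knowing the assigned dose, so the blind is kept. Nothing now covered is lost for study capsules: one capsule holds at most 80 mg, so exceeding 80 mg already takes more than one.

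**Sections 5.2 and 6.5.** Add current atomoxetine use by name to the exclusions and to the disallowed list, and state that other stable ADHD drugs are permitted exceptions to the monoamine rule. With that in place, 8.5 needs no separate limit on atomoxetine from all sources.

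**Cost.** A few words in three sections by protocol amendment and one eCRF definition. Possibly a few fewer children will be eligible, and a few more symptom-free events will have to be documented. The analysis does not change.

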**Overall Design:**

This is a randomized, double blind, cross-over study of the combination of atomoxetine and oxybutynin (ato-oxy) in children with DS and OSA documented by polysomnography (PSG). Participants will receive high dose ato-oxy for four weeks as well as low dose ato-oxy for four weeks in random order. During the high dose ato-oxy period, participants will take 5 mg oxybutynin and 0.5mg/kg/day (max 40 mg) atomoxetine nightly for one week. Atomoxetine dose will then be increased to 1.2 mg/kg/day (max 80 mg). During the low dose ato-oxy period, participants will take 5 mg oxybutynin and 0.5mg/kg/day (max 40 mg) atomoxetine. Dosing of the study treatment will occur approximately 30 minutes prior to bedtime. Participants who withdraw from the study will not be replaced.

Study participants will undergo eligibility screening that will include an initial screening to determine whether non- PSG enrollment criteria are met, followed by a 1-night in-lab PSG and health-related quality of life assessment for participants who qualify based on non-PSG criteria. For participants who are eligible and enroll in the study, the screening PSG night will serve as the baseline measure for apnea-hypopnea index (AHI) and other PSG endpoints. On the final night of dosing for both high dose ato-oxy and low-dose ato-oxy, participants will return for inpatient PSG and health-related quality of life assessment. The primary efficacy endpoint is the change in obstructive AHI from baseline (high dose ato-oxy vs. low dose ato-oxy).

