## 4.3 Justification for Dose

The prior study of ato-oxy in adults used a dosing regimen of 80 mg atomoxetine and 5 mg oxybutynin given at night (Taranto-Montemurro, Messineo et al. 2018). Based on the atomoxetine package insert, the pediatric weight-based equivalent for 80 mg atomoxetine is 1.2 mg/kg. Additionally, package insert dosing suggests starting at 0.5 mg/kg (max 40 mg) and increasing to 1.2 mg/kg (max 80 mg) after a minimum of three days. Given this, for high dose ato-oxy, participants will be titrated from 0.5 mg/kg to 1.2 mg/kg atomoxetine after one week on 0.5 mg/kg therapy to reduce the risk of adverse effects. For low dose ato-oxy, we will use the package insert suggested starting dosing of 0.5 mg/kg (max 40 mg). This will allow the evaluation of a lower atomoxetine dose, which may be associated with fewer adverse events. Recommended dosing of oxybutynin in children >5 years old starts at 5 mg twice daily for

overactive bladder and the planned oxybutynin dose for this proposal is 5 mg once at night. Therefore, we did not consider it necessary to include a lower dose of oxybutynin, as the dose used in this proposal is already lower than the current FDA-approved dose recommendation.

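### Section 6.5 is ambiguous for a child already taking atomoxetine, and on one reading the study dose is added to the home dose

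*Combined protocol and SAP*

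**What the plan says.** Section 2.2.3 describes the study drug this way: "Atomoxetine is a pre-synaptic norepinephrine reuptake inhibitor indicated for the treatment of attention deficit hyperactivity disorder in children and adults". A child on home atomoxetine is therefore a child on ADHD medication.

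Two entries in section 6.5 touch that child. The list of disallowed drugs opens with "MAOIs or other drugs that affect monoamine concentrations". The list of permitted drugs ends with "Patients currently on medications for Attention Deficit Hyperactivity Disorder will be included, but should not change their medication regimen/dosage during the study". Neither entry refers to the other, and no order of precedence is given.

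The exclusions in section 5.2 include use of an MAO inhibitor but do not mention atomoxetine. Home oxybutynin is treated differently: section 6.5 disallows "Anticholinergics and anticholinesterase inhibitors, including drugs with substantial anticholinergic side effects", and no later entry reverses that.

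On dosing, section 4.1 sets study atomoxetine at 0.5 mg/kg/day (maximum 40 mg) in the low period. In the high period it is 1.2 mg/kg/day (maximum 80 mg) after one week at the lower dose. Section 6.6 says "Through protocol amendment, planned doses may be decreased on an individual or group basis". Section 8.5 treats "any dose of atomoxetine greater than 80 mg" as an overdose and leaves dose interruption or modification to the investigator.

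**The concern.** The medication review at Visit 1 would find the home drug, but section 6.5 then offers the site two answers. One keeps the child out or stops the drug. The other enrolls the child and asks that the home dose stay as it is. No text requires a home dose of atomoxetine to be stopped, washed out or subtracted from the study dose.

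The main stake is safety. The protocol itself names urinary retention, heart rate and blood pressure effects (section 8.3) and the boxed warning on suicidal ideation (section 8.3.3) as matters to watch. Section 4.3 justifies the one-week titration as a way to reduce adverse effects. A child on 1.2 mg/kg at home would start study treatment at a total of 1.7 mg/kg, so that protection would be lost.

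There is a smaller design consequence. For such a child the two periods would not test the planned total doses. The entry decision in section 5.2, which excludes a total AHI below 5, would rest on a polysomnogram recorded on active drug.

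**Working it through.** The plan gives no figure on this point to reproduce. The check compares the possible readings and then works out the dose on the permissive one.

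**Readings of section 6.5 for a child on home atomoxetine**
- Monoamine entry read broadly and given priority: the child is barred, which goes against the statement that children on ADHD medication are included.
- ADHD entry taken as a specific exception: the child enters on an unchanged home dose, and nothing carves out the study drug.
- Monoamine entry read narrowly, since its only example is rasagiline: the conflict weakens, but then nothing bars home atomoxetine at all.

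**Inputs**
- Study doses and caps: section 4.1, as above.
- Home dose: not in the documents. Assumed to lie in the label range cited in section 4.3, from 0.5 mg/kg (cap 40 mg) to 1.2 mg/kg (cap 80 mg).
- Overdose line: 80 mg (section 8.5), read as a daily total because the doses in section 4.1 are per day.
- Nights: 28 per period, of which 28 − 7 = 21 are at the full high dose.

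**Formula**, for weight w in kg: total = min(home mg/kg × w, home cap) + min(study mg/kg × w, study cap).

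| Home dose | Period | Total below the caps (mg/kg) | Passes 80 mg above | Largest total |
|---|---|---|---|---|
| 0.5 mg/kg | low | 0.5 + 0.5 = 1.0 | never | 40 + 40 = 80 mg |
| 0.5 mg/kg | high | 0.5 + 1.2 = 1.7 | 80/1.7 = 47.1 kg | 40 + 80 = 120 mg |
| 1.2 mg/kg | low | 1.2 + 0.5 = 1.7 | 80/1.7 = 47.1 kg | 80 + 40 = 120 mg |
| 1.2 mg/kg | high | 1.2 + 1.2 = 2.4 | 80/2.4 = 33.3 kg | 80 + 80 = 160 mg |

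The caps begin to bind at 80/1.2 = 66.7 kg and 40/0.5 = 80 kg, so they do not alter the weight thresholds. The 160 mg maximum needs 66.7 kg or more.

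**Examples at a home dose of 1.2 mg/kg**
- 40 kg: 48 + 48 = 96 mg in the high period (planned 48) and 48 + 20 = 68 mg in the low period (planned 20).
- 25 kg: 30 + 30 = 60 mg in the high period (planned 30). This is double the plan, yet below a line fixed in mg.
- Nights over the line: 21 of 56 for a child between 33.3 and 47.1 kg, and all 56 for a heavier child. The titration week also totals 1.7 mg/kg, so it counts only above 47.1 kg.

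**Effect on the contrast.** For home dose h the between-period difference below the caps is (h + 1.2) − (h + 0.5) = 0.7 mg/kg, as planned. The high-to-low ratio falls from 1.2/0.5 = 2.4 to 1.7/1.0 = 1.70 (home 0.5) or 2.4/1.7 = 1.41 (home 1.2).

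**The case against.** The strongest reply is that the protocol, read as a whole, does not contemplate double dosing. Section 4.1 states what participants take per day, with daily maxima, and a home dose on top exceeds that regimen at any weight. It also describes the gap between periods as two weeks without drug, which fits poorly with continued home atomoxetine. The disallowed list is unqualified. The ADHD entry sits under a heading for drugs that are only generally allowed and lack substantial CNS effects. All of this stands as evidence of intent. It does not close the gap: no sentence bars the home drug, the ADHD entry is specific in its favor, and section 10.1.12 asks sites to follow the protocol exactly.

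Two stronger readings might be inferred, and the text does not support them.
- That section 6.5 flatly contradicts itself. This depends on the broad reading of an entry whose only example is rasagiline and whose bracketed note concerns MAO inhibitors. Ambiguity is the accurate description.
- That the site has no way to deal with the overlap. Section 7.1 lets the investigator change management after a clinically significant finding, and section 8.5 leaves dose interruption or modification to the investigator after an overdose. Both act after the event, so they mitigate the overlap and do not prevent it. Section 8.5 is also not triggered in a lighter child whose total stays at or below 80 mg.

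**Conclusion.** The point holds as an ambiguity with an avoidable dosing hazard. If the ADHD entry is followed, total atomoxetine is 1.7 to 2.4 mg/kg in the high period and 1.0 to 1.7 mg/kg in the low period, against planned 1.2 and 0.5. At a home dose of 1.2 mg/kg the 80 mg line is passed above 33.3 kg (high) and 47.1 kg (low).

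These figures rest on an assumed home dose, on reading the 80 mg line as a daily total, and on a site choosing the permissive reading. The documents do not say how many such children would enroll, so the frequency is unknown. Duplicate dosing is one possible reading and not a planned procedure.

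A reader might also infer that the primary comparison is biased or loses power. The documents do not support that. The planned dose difference between periods is preserved within the child, and with untransformed changes the shared baseline cancels. Any loss of effect would need dose-response data and a count of such children, and neither is given. The change is a cheap improvement and is worth making for safety.

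**What to change.** Add current use of atomoxetine to the study-entry exclusions in section 5.2. Reword the ADHD entry in section 6.5 to cover ADHD medications other than atomoxetine, and state that it is an exception to the monoamine entry. Keep the unchanged-regimen rule for those drugs. Check this after consent, in the pre-screening that footnote 1 of the Schedule of Activities already allows before Visit 1, so that the child is identified before the baseline polysomnogram.

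The cost is one exclusion line and one reworded entry, with no extra visit or test. The downside is that children on atomoxetine become ineligible. Those who have already consented count as screen failures, and section 5.6 allows rescreening only if a protocol amendment enables it; the amendment that adds the exclusion could do so. Children on other ADHD drugs still enter.
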